Appendix C. Sample Serious Adverse Event Form (DO NOT USE)

 evolocumab (AMG 145) 20120138	Clinical Trial Serious Adverse Event Report (3-IMP) Notify Amgen Within 24 Hours of knowledge of the event	 New  Follow-up												
SELECT OR TYPE IN A FAX NUMBER														
1. SITE INFORMATION														
Site Number	Investigator	Country												
Reporter	Phone Number () ()	Fax Number () ()												
2. SUBJECT INFORMATION														
Subject ID Number	Date of Birth Day Month Year	Sex  F  M Race												
3. SERIOUS ADVERSE EVENT - Information in this section must also be entered on the Serious Adverse Event Summary CRF														
Provide the date the Investigator became aware of this Serious Adverse Event Information: Day Month Year														
Serious Adverse Event Diagnosis or Syndrome If diagnosis is unknown, enter Signs / Symptoms When Final Diagnosis is known, enter as Adverse Event List one event per line. If event is fatal, enter the Cause of Death. Entry of "Death" is not acceptable, as this is an outcome.	Date Started Day Month Year	Date Ended Day Month Year	Potential Endpoint? No Yes	Check only if event occurred before first dose of IP	Enter Serious Criteria code (see codes below)	Is there a reasonable possibility that the event may have been caused by If yes see section 10	Relationship Pre-filled autoinjector /pen (AI/pen) 3.5 mL personal injector	Outcome of Event 01 Resolved 02 Resolving 03 Not resolved 04 Fatal	Check only if event is related to study procedure eg, biopsy					
Serious Criteria: 01 Fatal 02 Immediately life-threatening	03 Required hospitalization 04 Prolonged hospitalization	05 Persistent or significant disability /incapacity 06 Congenital anomaly / birth defect	07 Other significant medical hazard											
4. HOSPITALIZATION			Date Admitted Day Month Year			Date Discharged Day Month Year								
Was subject hospitalized?  No  Yes, if yes, please complete date(s):														
5. INVESTIGATIONAL PRODUCT (IP)			Initial Start Date Day Month Year			Prior to, or at time of Event Date of Dose Day Month Year			Dose Route Frequency			Action Taken with Product 01 Still being Administered 02 Permanently discontinued 03 Withheld		
evolocumab (AMG 145)  Open Label														
Pre-filled autoinjector/pen (AI/pen)  Open Label														
3.5 mL personal injector  Open Label														
6. CONCOMITANT MEDICATIONS (eg, chemotherapy)			Any Concomitant Medications?  No  Yes, If yes, please complete:											
Medication Name(s)	Start Date Day Month Year	Stop Date Day Month Year	Co-suspect No Yes	Continuing No Yes	Dose	Route	Freq.	Treatment Med No Yes						

 evolocumab (AMG 145) 20120138	Clinical Trial Serious Adverse Event Report (3-IMP) Notify Amgen Within 24 Hours of knowledge of the event	 New  Follow-up
---	---	--

	Site Number	Subject ID Number	
--	-------------	-------------------	--

7. RELEVANT MEDICAL HISTORY *(include dates, allergies and any relevant prior therapy)*

8. RELEVANT LABORATORY VALUES *(include baseline values)* Any Relevant Laboratory values? No Yes. If yes, please complete:

Date	Test			Unit																	
	Date																				
	Day	Month	Year																		

9. OTHER RELEVANT TESTS *(diagnostics and procedures)* Any Other Relevant tests? No Yes. If yes, please complete:

Date	Additional Tests	Results	Units

10. CASE DESCRIPTION *(Provide narrative details of events listed in section 3)* For each event in section 3, where relationship=Yes, please provide rationale.

Signature of Investigator or Designee	Title	Date
---------------------------------------	-------	------

FORM-065033 Clinical Trial SAE Report (3-IMP) V5.0 Effective date: 20-August-2014 (This is a variant of parent FORM-015482)
 SAER Created: 21-AUG-2014 Page 2 of 2

Appendix D. Pregnancy and Lactation Notification Worksheets

AMGEN[®] Pregnancy Notification Worksheet

Fax Completed Form to the Country-respective Safety Fax Line

SELECT OR TYPE IN A FAX#

1. Case Administrative Information

Protocol/Study Number: _____

Study Design: Interventional Observational (If Observational: Prospective Retrospective)

2. Contact Information

Investigator Name _____ Site # _____

Phone (____) _____ Fax (____) _____ Email _____

Institution _____

Address _____

3. Subject Information

Subject ID # _____ Subject Gender: Female Male Subject DOB: mm ____ / dd ____ / yyyy ____

4. Amgen Product Exposure

Amgen Product	Dose at time of conception	Frequency	Route	Start Date
				mm ____ / dd ____ / yyyy ____

Was the Amgen product (or study drug) discontinued? Yes No

If yes, provide product (or study drug) stop date: mm ____ / dd ____ / yyyy ____

Did the subject withdraw from the study? Yes No

5. Pregnancy Information

Pregnant female's LMP mm ____ / dd ____ / yyyy ____ Unknown

Estimated date of delivery mm ____ / dd ____ / yyyy ____ Unknown N/A

If N/A, date of termination (actual or planned) mm ____ / dd ____ / yyyy ____

Has the pregnant female already delivered? Yes No Unknown N/A

If yes, provide date of delivery: mm ____ / dd ____ / yyyy ____

Was the infant healthy? Yes No Unknown N/A

If any Adverse Event was experienced by the infant, provide brief details: _____

Form Completed by

Print Name: _____

Title: _____

Signature: _____

Date: _____

Amgen maintains a Pregnancy Surveillance Program that collects data about pregnancy of women who have been exposed to an Amgen product directly or via male sexual partner. Information from this program and from other sources of information, will contribute to knowledge that ultimately could help patients and their doctors in the future make more informed decisions about taking an Amgen medication during pregnancy.

AMGEN Lactation Notification Worksheet

Fax Completed Form to the Country-respective Safety Fax Line
SELECT OR TYPE IN A FAX#

1. Case Administrative Information														
Protocol/Study Number: _____														
Study Design:  Interventional  Observational (If Observational:  Prospective  Retrospective)														
2. Contact Information														
Investigator Name _____		Site # _____												
Phone (____) _____		Fax (____) _____		Email _____										
Institution _____														
Address _____														
3. Subject Information														
Subject ID # _____ Subject Date of Birth: mm ____ / dd ____ / yyyy ____														
4. Amgen Product Exposure														

Amgen Product	Dose at time of breast feeding	Frequency	Route	Start Date	

 	 	 	 	mm ____ / dd ____ / yyyy ____	

					Amgen Product	Dose at time of breast feeding	Frequency	Route	Start Date					mm ____ / dd ____ / yyyy ____
Amgen Product	Dose at time of breast feeding	Frequency	Route	Start Date										
				mm ____ / dd ____ / yyyy ____										
Was the Amgen product (or study drug) discontinued?  Yes  No														
If yes, provide product (or study drug) stop date: mm ____ / dd ____ / yyyy ____														
Did the subject withdraw from the study?  Yes  No														
5. Breast Feeding Information														
Currently breast feeding?  Yes  No														
If No, provide stop date: mm ____ / dd ____ / yyyy ____														
Infant date of birth: mm ____ / dd ____ / yyyy ____														
Infant gender:  Female  Male														
Is the infant healthy?  Yes  No  Unknown  N/A														
If any Adverse Event was experienced by the mother or the infant, provide brief details: _____														

Form Completed by:														
Print Name: _____		Title: _____												
Signature: _____		Date: _____												

Amgen maintains a Lactation Surveillance Program that collects data about women who have been exposed to an Amgen product prior to conception, during pregnancy, and during lactation. Information from this program and from other sources of information will contribute to knowledge that ultimately could help patients and their doctors in the future make more informed decisions about taking an Amgen medication during lactation.

Effective Date: _____

Amendment 6

Title: A Multicenter, Controlled, Open-label Extension (OLE) Study to Assess the Long-term Safety and Efficacy of AMG 145

Amgen Protocol Number: 20120138

EudraCT Number: 2012-004357-83

OSLER 2

Open Label Study of Long Term Evaluation Against LDL-C Trial

Amendment 1 Date : 12 February 2013

Amendment 2 Date: 30 April 2013

Superseding Amendment 2 Date: 23 May 2013

Amendment 3 Date: 15 November 2013

Superseding Amendment 3 Date: 15 February 2014

Superseding Amendment 3 Date: 24 February 2014

Amendment 4 Date: 15 April 2014

Amendment 5 Date: 19 December 2014

Amendment 6 Date: 03 April 2015

Rationale:

This document provides the rationale and detailed list of changes for Amendment 6, dated 03 April 2015, from Amendment 5 of the study protocol, dated 19 December 2014.

The purpose of the amendment is to:

- Update [exclusion criteria](#) to include methods of effective birth control in the protocol language

Description of Changes:

[Section: Header](#)

Replace:

19 December 2014

With:

03 April 2015

[Section: Coverage](#)

Add:

Amendment 6 Date: 03 April 2015

[Section: 4.2 Exclusion Criteria](#)

Second Criterion, Bullet point 2

Replace:

- Acceptable methods of effective contraception are defined in the ICF. Where required by local laws, regulations and/or guidelines, additional country-specific requirements are outlined in a country-specific protocol supplement.

With:

- **Acceptable methods of effective birth control include: sexual abstinence (when this is in line with the preferred and usual lifestyle of the subject [periodic abstinence (eg, calendar, ovulation, symptothermal, post-ovulation methods), declaration of abstinence for the duration of a trial, and withdrawal are not acceptable methods of contraception]), surgical contraceptive methods (vasectomy or bilateral tubal ligation), use of hormonal birth control methods (pills, shots, implants or patches), intrauterine devices (IUDs), or two (2) barrier methods (each partner must use one barrier method) with spermicide – males must use a condom with spermicide; females must choose either a diaphragm with spermicide, OR cervical cap with spermicide, OR contraceptive sponge with spermicide. Note: Additional medications given during treatment with evolocumab may alter the contraceptive requirements. These additional medications may require an increase in the number of contraceptive methods and/or length of time that contraception is to be utilized after the last dose of protocol-required therapies. The investigator is to discuss these contraceptive changes with the study subject.**

Amendment 5

Title: A Multicenter, Controlled, Open-label Extension (OLE) Study to Assess the Long-term Safety and Efficacy of AMG 145

Amgen Protocol Number: 20120138
EudraCT Number: **2012-004357-83**

OSLER 2

Open Label Study of Long Term Evaluation Against LDL-C Trial

Amendment 5 Date: 19 December 2014

Rationale:

This document provides the rationale and detailed list of changes for Amendment 5, dated 19 December 2014, from amendment 4 of the study protocol, dated 15 April 2014.

The purpose of the amendment is to:

- Extend the treatment duration of the study by an additional 1 year to further characterize the safety and tolerability of evolocumab(AMG 145) over 3 years of exposure consistent with the primary objective for this study.
- Update the expected sample size to account for additional studies that are scheduled to complete to permit the timely analysis and disclosure of results. Rather than extend the duration of other studies allowing patients into this open label extension study will contribute to the evidence for safety and tolerability of up to 3 years of exposure of evolocumab
- Update the schedule of assessments and schema for clarification and ease of use
- Update exclusion criteria regarding effective methods of birth control to align with current Amgen standards, it is noted that this change is not a consequence of a change in the safety profile of evolocumab.
- Clarify definition of Investigational Product (IP) as combination product of evolocumab (AMG 145) and device with term Investigational Medicinal Product (IMP) used to refer to evolocumab (AMG 145) to align with standards provided by CMC Safety
- Clarify reporting process for adverse events and serious adverse events
- Update process for Pregnancy and Lactation Reporting
- Remove the external data monitoring committee (DMC) following the DMC's expressed preference to not review open-label, uncontrolled safety data. Safety monitoring will continue to be performed by AMGEN. Even though review of this specific study would no longer fall under direct DMC review, the DMC will continue to consider the totality of data from all studies. Any emerging safety considerations identified by AMGEN would be discussed with the DMC and the

committee would incorporate that data when making its recommendations to AMGEN.

- Minor other updates, clarifications and corrections

Amendment 4

Title: A Multicenter, Controlled, Open-label Extension (OLE) Study to Assess the Long-term Safety and Efficacy of AMG 145

Amgen Protocol Number:20120138

EudraCT Number: **2012-004357-83**

OSLER 2

Open Label Study of Long Term Evaluation Against LDL-C Trial

Amendment 4 Date: 15 April 2014

Rationale:

This document provides the rationale and detailed list of changes for Amendment 4, dated 15 April 2014, from superseding amendment 3 of the study protocol, dated 24 February 2014.

The purpose of the amendment is to:

- Update the schedule of assessments schema for clarification and ease of use
- Add a patient questionnaire for patients experiencing a change in the device used to deliver AMG 145
- Minor other updates, clarifications and corrections

Amendment 3

Title: A Multicenter, Controlled, Open-label Extension (OLE) Study to Assess the Long-term Safety and Efficacy of AMG 145

Amgen Protocol Number: 20120138
EudraCT Number: 2012-004357-83

OSLER 2

Open Label Study of Long Term Evaluation Against LDL-C Trial

Goal Achievement after Utilizing an anti-PCSK9 antibody in Statin Intolerant Subjects

Amendment Date: 15 November 2013

Superseding Amendment Date: 15 February 2014

Superseding Amendment Date: 24 February 2014

Rationale:

This document provides the rationale and detailed list of changes for Amendment 3, dated 24 February 2014, from superseding amendment 2 of the study protocol, dated 23 May 2013.

The purpose of the amendment is to:

- Add Vitamin E reflex testing to the protocol in cases where LDL-C is < 25 mg/dL.
- Add language for the use of the 3.5 mL personal injector. The 3.5 mL Personal Injector will only be made available for use in this study once it has been determined that the intended user population for AMG 145 can safely and effectively use the device in clinical trials under guidance of study investigators.
- The schedule of assessments and schema were clarified and changed in format to be easier to use
- The body of the protocol and schedule of assessments were updated and made consistent
- The visit schedule was clarified to list the exact timing of the visit, replacing reference to quarterly visits
- The protocol now references the latest IB (2013)
- The protocol now includes "Investigator Responsibilities for Data Collection"
- Non-coronary revascularizations will no longer be collected (update to be consistent with DMC charter)
- Minor other updates, clarifications and corrections

Amendment 2 - Superseding Amendment

Protocol Title: “A Multicenter, Controlled, Open-label Extension (OLE) Study to Assess the Long-term Safety and Efficacy of AMG 145”

Amgen Protocol Number **AMG 145 20120138**

Amendment Date: 23 May 2013

Rationale:

This protocol is being amended to support feedback received from VHP to include a minor administrative change to Protocol Amendment 2.

Description of Changes:

Section: Study Schema

Changes:

- Addition of one blue triangle on Day 1 indicating in-clinic administration of IP.

Amendment 1

Protocol Title: “A Multicenter, Controlled, Open-label Extension (OLE) Study to Assess the Long-term Safety and Efficacy of AMG 145”

Amgen Protocol Number **AMG 145 20120138**

Amendment Date: 12 February 2013

Rationale:

This protocol is being amended to support feedback received from FDA and our Data Monitoring Committee (DMC) to include a standard of care (SOC) group for the first year. Doing so increases the scientific rigor of the study and reduces undue relatedness and causality of adverse events in subjects receiving AMG 145.

Additional major changes include:

- Reduction to 2 years duration – to facilitate cost containment as 2+ year data will be captured through other OLE/Outcomes studies.
- Inclusion of Q2W dose regimen – for consistency with other Phase 3 studies and opportunity to allow subjects to experience different dosing regimens
- Alignment of assessments with other approved longer term AMG 145 studies, eg, 118 - for consistency with other Phase 3 studies and pooling of data
- Addition of extra visits for AMG 145 naïve subjects requiring training on use of prefilled AI/pen – to improve opportunity for successful in-home use administration of AMG 145

IVRS	Interactive voice response system
LDL-C	Low density lipoprotein cholesterol
LFT	Liver Function Test
Lp(a)	Lipoprotein(a)
MedDRA	Medical dictionary for regulatory activities
OLE	Open label extension
QM	Every month
Q2W	Every 2 weeks
SOC	Standard of care
SAP	Statistical analysis plan
TIA	Transient ischemic attack
ULN	Upper limit of normal
VLDL-C	Very low density lipoprotein cholesterol

1. Introduction

The purpose of this interim SAP is to pre-specify interim analyses to support regulatory filings. The analysis strategy is consistent with the protocol specified analysis. Analyses will be performed based on datasets of an ongoing study 20120138, entitled A Multicenter, Controlled, Open-label (OLE) Study to Assess the Long-term Safety and Efficacy of AMG 145 (latest amendment 2 is 30 APR 2013).

2. Objectives

The objective for this analysis is to summarize the safety and lipid data collected up to a cutoff date reported in the table outputs for subjects rolled over from parent studies into the extension study 20120138. All data prior to the data cut date will be collected, checked and queried in the similar fashion as the final database lock.

3. Endpoints

3.1 Primary Endpoint

Subject incidence of Adverse Events (AEs).

3.2 Secondary Endpoints

- Percent change from baseline in LDL-C at each visit with planned lipid measurements
- Change from baseline in LDL-C at each visit with planned lipid measurements
- Percent change from parent study EOS in LDL-C at each visit with planned lipid measurements
- Change from parent study EOS in LDL-C at each visit with planned lipid measurements

3.3 Exploratory Endpoints

- Subject incidence of adjudicated events and non-coronary revascularization
 - Death (all cause, cardiovascular)
 - Cardiac ischemic events (myocardial infarction, hospitalization for unstable angina, coronary revascularization)
 - Hospitalization for heart failure
 - Cerebrovascular events (transient ischemic attack, stroke)
 - Non-coronary revascularization
- Change and percent change from baseline and from parent study EOS at each scheduled visit in each of the following lipid and other lab parameters
 - Non-HDL-C
 - ApoB
 - Total cholesterol/HDL-C ratio
 - Total cholesterol

- ApoB/ApoA1 ratio
- Lp(a)
- Triglycerides
- HDL-C
- VLDL-C
- ApoA1
- High sensitivity C-reactive protein (hsCRP)

3.4 Other Safety Endpoints

- Changes from baseline in safety laboratory values (including HbA1c) and vital signs at each scheduled visit.
- **Development of anti-AMG 145 antibodies**

4. Hypothesis

The primary clinical hypothesis is that long-term exposure of AMG 145 will be safe and well-tolerated in subjects with primary hyperlipidemia and subjects with mixed dyslipidemia.

5. Definitions

5.1 Study Time Points

Baseline

For variables other than sex, race, country, region, and baseline metabolic syndrome, baseline is defined as the parent study baseline. Note that baseline metabolic syndrome will be using parent study baseline information, but with updated sex and race from the extension study data.

First Dose Date

For subjects randomized to AMG 145+SOC, the first dose date is the first date at which the subject was administered IP. For subjects randomized to SOC, the first dose date is the first date at which the subject was administered IP at or after the Week 48 clinical visit.

End of Investigational Product (EOIP) Date

If a subject has completed or discontinued IP, the EOIP date is the date recorded on the final IP dose date eCRF.

End of Study (EOS) Date

For each subject, the End of Study Date is the date recorded on the End of Study eCRF.

Enrollment Date

The enrollment date for a subject is either the subject's EOS date for the parent study or the date that subject has signed the ICF for Study 20120138, whichever is later.

Randomization Date

The randomization date for each subject is the date the investigator (or designee) confirms in the IVRS that the subject has met all eligibility criteria and is randomized.

Study Day 1

For subjects randomized to AMG 145+SOC arm and received at least one dose of AMG 145, Study Day 1 is defined as the first day that AMG 145 is administered during this study.

For subjects randomized to SOC only arm, or randomized to AMG 145+SOC arm but never received AMG 145, Study Day 1 is defined as the day of randomization.

Study Day

For each subject, and for a given study visit date, study day is defined as the number of days since Study Day 1:

$$\text{Study day} = (\text{study visit date} - \text{Study Day 1 date}) + 1$$

If the date of interest is prior to the Study Day 1:

$$\text{Study day} = (\text{study visit date} - \text{Study Day 1 date})$$

SOC-Controlled period

The start of the SOC-Controlled period is Study Day 1.

For the end of the SOC-Controlled period:

- If a subject is administered a dose of IP at Week 48, the day prior to the week 48 IP date is the end of the SOC-Controlled period.
- If a subject is not administered a dose of IP at Week 48, the SOC-Controlled period will end the earliest of Study Day 343, the EOS date, or data cutoff date.

All-IP period

Subjects with EOS dates or data cutoff dates \leq end of SOC-Controlled period dates will have missing start and end of All-IP period dates.

Otherwise:

- All-IP period start date = end of SOC-Controlled period date+1.
- All-IP period end date = EOS date or the data cutoff date, whichever occurred earlier.

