10.1.5 Analysis Sets

The full analysis set (FAS) will include all subjects randomized in this study. All analyses of the randomized controlled period of the study will be performed using the FAS. Analyses of the period after the randomized controlled period may be limited to those receiving investigational product.

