5.3 Other Study Related Definitions

Analytical Study Week Assignments

Analytical windows will be used to assign parameters to study weeks. The Algorithm is provided in [Appendix A](#).

IP Exposure Period in Months

IP Exposure = $[(\min(\text{EOIP date} + 28 \text{ days}, \text{EOS date}, \text{data cutoff date}) - \text{First dose date}) + 1] / 365.25 * 12$. For subjects randomized to SOC treatment during the SOC-Controlled period, the first dose date is equivalent to the first dose date during the All-IP period.

Study Exposure Period in Months

For each randomized subject, Study Exposure Period = $[\min(\text{EOS date}, \text{data cutoff date}) - \text{enrollment date}] + 1 / 365.25 * 12$

IP Exposure in Months During the SOC-Controlled period

For subjects randomized to AMG 145+SOC arm and received at least one dose of AMG 145 in the SOC-Controlled period, IP Exposure during the SOC-Controlled period = $[(\min(\text{EOIP date} + 28 \text{ days}, \text{end of SOC-Controlled period}) - \text{Study Day 1}) + 1] / 365.25 * 12$. Any IP exposure < 0 will be considered as N/A.

For subjects randomized to SOC or randomized to AMG 145 + SOC and not dosed in the SOC-Controlled period, IP Exposure during the SOC-Controlled period = N/A.

IP Exposure in Months During the All-IP period

For each randomized subject in the Interim All-IP period Analysis Set, IP Exposure during the All-IP period

= $[(\min(\text{EOIP} + 28 \text{ days}, \text{end of All-IP period}) - \text{start date of All-IP period}) + 1] / 365.25 * 12$. If the above calculation is < 0 , then set to 0.

Study Exposure in Months During the SOC-Controlled period

For each randomized subject, Study Exposure Period for the SOC-Controlled period = $[(\text{end of SOC-Controlled period date} - \text{start of the SOC-Controlled period}) + 1] / 365.25 * 12$.

Study Exposure in Months During the All-IP period

For each randomized subject that received a dose of IP during the All-IP period,

Study Exposure Period for the All-IP period = $[(\text{end of All-IP period} - \text{start of the All-IP period}) + 1] / 365.25 * 12$.

Adverse Events Included in the Summary Tables

An adverse event is included in SOC-Controlled period summaries if it occurs during the SOC-Controlled period and the subject is in the Interim SOC-Controlled period Analysis Set.

An adverse event is included in All-IP period summaries if it occurs during the All-IP period and the subject is in the Interim All-IP period Analysis Set.

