Sex

For subjects that enroll in an extension study, the subject's sex is the sex recorded on the extension study eCRF. For other subjects, the subject's sex is the sex recorded on the parent study eCRF.

Race

For subjects that enroll in an extension study, the subject's race is the race recorded on the extension study eCRF. For other subjects, the subject's race is the race recorded on the parent study eCRF.

Country and Region

For subjects that enroll in an extension study, the subject's country and region are those recorded in the extension study. For other subjects, the subject's country and region are those recorded in the parent study.

Baseline Metabolic Syndrome

For each subject without type 2 diabetes mellitus, metabolic syndrome is identified by the presence of 3 or more of the components listed below (modified AHA/NHLBI criteria). Subjects with type 2 diabetes cannot be categorized as having metabolic syndrome.

Risk Factor	Defining Level
Elevated waist circumference:	
Non-Asian:	
Men	≥ 102 cm
Women	≥ 88 cm
Asian:	
Men	≥ 90 cm
Women	≥ 80 cm
Triglycerides	≥ 150 mg/dL
HDL cholesterol	
Men	< 40 mg/dL
Women	< 50 mg/dL
Blood pressure	SBP ≥ 130 mmHg or DBP ≥ 85 mmHg OR Hypertension checked 'yes' on CV Medical History eCRF
Fasting glucose	≥ 100 mg/dL

4-Level Treatment Group

All tables in this interim analysis will be summarized by randomized group (AMG 145+SOC vs. SOC alone). Since subjects received either AMG 145 or control treatment in parent study, the tables will be further categorized using the following 4 levels (parent study treatment group/current study treatment group): "AMG 145/AMG 145 + SOC"; "AMG 145/SOC Only"; "Control/AMG 145 + SOC", and "Control/SOC Only".

6. Analysis Subsets

Interim SOC-Controlled period Analysis Set

The Interim SOC-**C**ontrolled period **A**nalysis **S**et (ICOAS) will include all subjects randomized in this study who have at least 12 weeks of potential follow-up (eg. subjects for whom Data Cutoff Date - Study Date for Study Day 1 + 1 > 91 days); the restriction on potential follow-up is to prevent operational bias that may occur by the increased frequency of visits during the first 12 weeks of the study. Subjects will be analyzed according to the treatment group to which they were randomized during the SOC-Controlled period. All data from the SOC-Controlled period will be summarized, regardless of possible IP discontinuation.

Interim All-IP period Analysis Set

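### The controlled safety period starts at first dose for dosed AMG 145 + SOC subjects but at randomisation for all others, so dated pre-dose events in later-dosed subjects reach no AE table

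*SAP*

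**What the plan says.** SAP 5.1 gives Study Day 1 two meanings. For subjects randomised to AMG 145 + SOC who receive at least one dose, "Study Day 1 is defined as the first day that AMG 145 is administered during this study". The other definition covers the SOC-alone arm and subjects assigned to AMG 145 + SOC "but never received AMG 145, Study Day 1 is defined as the day of randomization".

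Three rules then depend on that date:

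- **Start of the controlled period** (SAP 5.1): "The start of the SOC-Controlled period is Study Day 1".
- **AE counting** (SAP 5.3): "An adverse event is included in SOC-Controlled period summaries if it occurs during the SOC-Controlled period", provided the subject is in the ICOAS. SAP 7.3.3 leaves out events whose complete dates fall outside these definitions. The All-IP period begins only after the controlled period has ended.
- **Entry to the ICOAS** (SAP 6): "Data Cutoff Date - Study Date for Study Day 1 + 1 > 91 days".

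The end of the period also follows Study Day 1. It is the day before the Week 48 dose if there is one; otherwise "the SOC-Controlled period will end the earliest of Study Day 343, the EOS date, or data cutoff date".

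On the protocol side, Section 10.1.5 says "The full analysis set (FAS) will include all subjects randomized in this study" and applies that set to the randomised period. Section 9.1.2 collects AEs from enrollment in both arms. Appendix A marks randomisation in the Day 1 column and defines Day 1 as the day of first IP administration.

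**The concern.** Subject incidence of adverse events is the primary endpoint, and the SOC-alone arm is there to give it a concurrent comparison. That comparison needs one time origin for everyone randomised. Here the origin depends on arm and, within the AMG 145 + SOC arm, on whether the subject is later dosed.

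An event between randomisation and first dose is collected on the eCRF. If the subject is then dosed, a dated event falls before the controlled period and never reaches the All-IP period, so it is in neither set of tables. If the subject is never dosed, it counts. If it happens to a SOC-alone subject on the same day after randomisation, it counts. Inclusion is thus decided by what happens after the event. A subject undosed at one data cutoff and dosed before the next would also change time zero between interim reports.

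The ICOAS rule applies its follow-up requirement to the same arm-specific date, so membership of the safety comparison also depends on arm for subjects near the threshold.

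**Working it through.** **Arm sizes and the protocol's own figure.** Protocol 10.2 gives 3478 + 950 = 4428 subjects. At 2:1 that is 1476 SOC-alone and 2952 AMG 145 + SOC. Exact (Clopper-Pearson) 95% intervals near 5% incidence are:

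- 74/1476: 3.96% to 6.25% (protocol: 4.0% to 6.3%)
- 148/2952: 4.25% to 5.86% (protocol: 4.3% to 5.9%)

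Both agree, so these sizes are used below.

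**What the date rules do.** Let g be the number of days from randomisation to first dose, and take a fully dated AE inside that interval.

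| Subject | Study Day 1 | In SOC-Controlled tables? | In All-IP tables? |
|---|---|---|---|
| SOC-alone | randomisation | yes | no |
| AMG 145 + SOC, never dosed | randomisation | yes | no |
| AMG 145 + SOC, dosed at day g | first dose | no | no |

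An AE whose date cannot be placed goes to the SOC-Controlled period in either arm (SAP 7.3.3), so the gap concerns dated events only.

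**ICOAS entry.** The condition cutoff − Study Day 1 + 1 > 91 means cutoff − Study Day 1 ≥ 91. Measured from randomisation:

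- SOC-alone and never-dosed AMG 145 + SOC: at least 91 days.
- Dosed AMG 145 + SOC: at least 91 + g days, which is 91 for g = 0, 92 for g = 1, 98 for g = 7 and 121 for g = 30.

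Take two subjects randomised 91 days before cutoff. The SOC-alone subject scores 91 + 1 = 92 > 91 and enters. An AMG 145 + SOC subject dosed one day after randomisation scores 90 + 1 = 91, which is not > 91, and does not enter.

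**Shifted or shortened.** The scheduled Week 48 day is 7 × 48 + 1 = 337, so a period ending the day before runs 336 days from Study Day 1. For a subject dosed at Week 48 it has the same nominal length in both arms, and in the AMG 145 + SOC arm it is moved g days later. It is shorter only where EOS or data cutoff comes first.

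**Illustrative size.** The documents give no distribution for g. Assume that every AMG 145 + SOC subject has the same g, with a constant hazard over 336 days. With 48-week risk p, the chance of an event in the gap is 1 − (1 − p)^(g/336). For p = 5% and g = 7 this is 1 − 0.95^(7/336) = 0.107%, and 0.00107 × 2952 ≈ 3.2 subjects.

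| g (days) | Subjects with an event in the gap, p = 5% | p = 50% (assumed) |
|---|---|---|
| 0 | 0 | 0 |
| 1 | 0.5 | 6.1 |
| 7 | 3.2 | 42 |
| 14 | 6.3 | 84 |
| 30 | 13.5 | 177 |

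These subjects may also have a later event that does count, so the table does not give the change in incidence. That change, for p = 5%, depends on the window:

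- Shifted window, constant hazard: none.
- Shifted window, hazard doubled in the first 30 days after randomisation (assumed): 0.09, 0.19 and 0.40 points lower for g = 7, 14 and 30.
- Window stopped 48 weeks after randomisation, constant hazard: 5% becomes 1 − 0.95^((336 − g)/336), which is 4.90%, 4.80% and 4.56%, or 0.10, 0.20 and 0.44 points lower.

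**The case against.** The strongest reply is that the planned gap is zero. Appendix A puts randomisation on Day 1, and Protocol 6.1.1 and 7.1.1 place supervised self-injection on that day. The protocol's 30-day window runs from the parent study's final visit to randomisation or Day 1, which is a different interval. All of this stands, and it limits the size of the problem. No passage caps the gap, however, and the SAP defines the two dates separately.

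Three stronger readings are tempting, and the documents do not support them:

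- *Pre-dose events count only against SOC-alone.* They also count for AMG 145 + SOC subjects never dosed, including a death before any dose.
- *The AMG 145 + SOC arm loses g days of follow-up*, such as 7/343 = 2.0% or 30/343 = 8.7%. The end of the period moves with Study Day 1, so the window is mainly shifted.
- *Both effects favour AMG 145.* The ICOAS rule removes a subject from numerator and denominator together. Those removed have short follow-up, so leaving them out could raise crude incidence. The direction is unknown.

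Two further replies bear on the remedy. SAP 6 justifies the 91-day rule by the denser visits of the first 12 weeks, which follow Day 1. Counted from randomisation, the rule would admit a subject randomised 91 days before cutoff and dosed 30 days later, with 61 days since first dose. And if only the start date moved, a subject dosed at Week 48 would have a window of about 336 + g days against 336 for SOC-alone. Both are fair, and the fix has to deal with them.

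Finally, the analyses are descriptive, so no error rate is at stake. That lowers the stakes but does not make the two arms' counting rules alike.

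**Conclusion.** The asymmetry is in the SAP's text and needs no assumption. A dated AE between randomisation and first dose is left out of both periods' tables if the AMG 145 + SOC subject is later dosed, and is counted for SOC-alone and never-dosed subjects. ICOAS entry inherits the same arm-specific date. This sits poorly with the protocol's all-randomised analysis of the controlled period.

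The effect is nil when first dose falls on the randomisation day, as scheduled, and is probably small otherwise. Its actual size cannot be computed, because the documents give neither the gap distribution nor the accrual pattern at cutoff. In the illustrations, a 7-day gap in every AMG 145 + SOC subject changes a 5% incidence by 0 to 0.10 points, depending on the assumed hazard and end rule. The point is a cheap improvement to the primary safety comparison; it is not evidence that the comparison is materially biased.

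**What to change.** - **SAP 5.1, controlled period:** for AE summaries, adjudicated-event summaries and Study Exposure, start the SOC-Controlled period at the randomisation date in both arms, and count the Day 343 limit from randomisation in both arms.
- **Period ending at the Week 48 dose:** report incidence with actual follow-up time (exposure-adjusted), so that a window of about 336 + g days is not compared crudely with one of 336.
- **SAP 6, ICOAS:** apply the 91-day rule from randomisation in both arms. Add the first-dose version as a sensitivity analysis, because the rule's stated purpose concerns early visit frequency.
- **Keep first dose** for IP exposure and for the Appendix A visit windows.
- **Report** the randomisation-to-first-dose gap in the AMG 145 + SOC arm and list the events that fall in it.

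The cost is SAP wording, one derived date, an exposure-adjusted summary and a short table. The randomisation date is already in the IVRS and AEs are already collected from enrollment. The downside is that a few pre-dose events will count in the AMG 145 + SOC arm, and its window may be slightly longer for late starters. If every subject was dosed on the day of randomisation, the common start date and entry rule change no counts.
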